### **7.3. Exclusion Criteria**

The presence of any of the following will exclude a subject from enrollment:

1. Subjects with primary central nervous system (CNS) malignancies or symptomatic central nervous system metastases. Subjects with brain metastases that have been previously treated and are stable for 6 weeks are allowed
2. Known acute or chronic pancreatitis
3. Any peripheral neuropathy  $\geq$  NCI CTCAE Grade 2
4. Persistent diarrhea or malabsorption  $\geq$  NCI CTCAE Grade 2, despite medical management
5. Impaired cardiac function or clinically significant cardiac diseases, including any of the following:
  - LVEF  $<$  45% as determined by MUGA scan or ECHO
  - Complete left bundle branch, or bifascicular block
  - Congenital long QT syndrome
  - Persistent or uncontrolled ventricular arrhythmias or atrial fibrillation
  - QTcF  $>$  460 msec on screening ECG (mean of triplicate recordings)
  - Unstable angina pectoris or myocardial infarction  $\leq$  3 months prior to starting CC-122

- Troponin-T value  $>0.4$  ng/mL or BNP  $>300$  pg/mL  
Subjects with baseline troponin-T  $>\text{ULN}$  or BNP  $>100$  pg/mL are eligible but must have cardiologist evaluation prior to enrollment in the trial for baseline assessment and optimization of cardioprotective therapy.
- Other clinically significant heart disease such as congestive heart failure requiring treatment or uncontrolled hypertension (blood pressure  $\geq 160/95$  mmHg)

6. Prior systemic cancer-directed treatments or investigational modalities  $\leq 5$  half lives or 4 weeks, whichever is shorter, prior to starting CC-122 or who have not recovered from side effects of such therapy. Luteinizing hormone-releasing hormone (LHRH) agonists will be allowed for subjects with metastatic prostate cancer
7. Major surgery  $\leq 2$  weeks prior to starting CC-122 or still recovering from post operative side effects
8. Women who are pregnant or breast feeding. Adults of reproductive potential not employing two forms of birth control as per PPRMP
9. Known human immunodeficiency virus (HIV) infection \*
10. Known acute or chronic hepatitis B or C virus infection \*\*
11. Status post solid organ transplant
12. Less than 100 days for subjects receiving autologous hematologic stem cell transplant (HSCT); or 6 months for subjects receiving allogeneic HSCT, or if otherwise not fully recovered from HSCT-related toxicity
  - a. The 6-month exclusionary period for recovery from HSCT-associated toxicity, applies regardless of whether an autologous or allogeneic transplant was performed
13. Known hypersensitivity to any component of the formulation of CC-122
14. Any significant medical condition (including active or controlled infection or renal disease), laboratory abnormality, or psychiatric illness that would prevent the subject from participating in the study
15. Any condition, including the presence of laboratory abnormalities, which places the subject at unacceptable risk if he/she were to participate in the study
16. Any condition that confounds the ability to interpret data from the study

\* HIV testing is not required at screening.

\*\* Refer to [Table 5](#) for exclusion based on hepatitis testing results.

## **8. DESCRIPTION OF STUDY TREATMENTS**

### **8.1. Description of Investigational Product(s)**

Please refer to the CC-122 Investigator's Brochure for detailed information concerning the physical properties of CC-122.

CC-122 will be supplied in two distinct formulations as follows: CC-122 AIC in 0.5, 1 and 3-mg strengths (equivalent to 0.44, 0.88, and 2.64 mg free base CC-122, respectively) and as CC-122 formulated capsules in 1, 3, 3.5 and 4-mg strengths (equivalent to 1.13, 3.38, 3.95 and 4.51 mg CC-122 HCl, respectively).

CC-122 AIC will be provided in white/white opaque gelatin capsules in strengths of 0.5 mg (size 4), 1 mg (size 3), and 3 mg (size 2). There are no excipients in the capsules.

The formulated capsules will be provided in reddish brown gelatin capsules in strengths of 1 mg (size 3), 3 (size 3), 3.5 mg (size 2) and 4 mg (size 2), containing the following excipients: Avicel PH 102, spray dried mannitol, crospovidone, areosil, and stearic acid.

The IP will be labeled per local regulations. Store as directed on the package label.

### **8.2. Treatment Administration and Schedule**

CC-122 is administered orally, on a 5 continuous days out of 7 days per week intermittent dosing schedule.

Each dose will be taken in the morning, with the subject having fasted overnight (minimum of 6 hours) and for one hour after dosing. Every effort should be made to ensure that subjects are adequately hydrated prior to dosing, such as ensuring that capsules are swallowed with at least 8 ounces of water (approximately 240 mL), and hydration levels should be adjusted according to age and clinical status.

Breakfast will be delayed until at least one hour after dosing. The site will record the time of the first meal after dosing for clinic visits with PK collection time points.

Doses will be administered in an escalating manner following satisfactory review of safety data from the lower doses. Within each cohort, enrollment will be staggered 24 hours or more between Cycle 1 Day 1 visits for each subject.

#### **8.2.1. Safety Review Committee**

The SRC will review the safety and available PK data at the end of the DLT evaluation period for each cohort to determine whether dose escalation can occur, to confirm the dose level to be used in a subsequent cohort, and to determine the MTD/RP2D. The SRC will also review and approve intra-subject dose escalations.

SRC members will include the study investigators, the sponsor's medical monitor, safety physician or designee, clinical research scientist, and study manager. In addition, the study pharmacokineticist, statistician, and other relevant study team members may attend, if needed, and both internal and external experts may be consulted by the SRC, as necessary. The outcomes of SRC meetings will be documented, and the minutes distributed for SRC approval.

### **8.2.2. Definition of a Treatment Cycle**

Each subject will be administered oral doses of CC-122 starting from Cycle Day 1 on a 5 continuous days out of 7 days per week intermittent dosing schedule in 28-day cycles (DLT evaluation period = at least 28 days).

Subjects may continue to receive CC-122 for as long as they derive benefit from treatment as assessed by the investigator. In subsequent cycles, subjects are treated in 28-day cycles on a 5 continuous days out of 7 days per week intermittent dosing schedule.

### **8.2.3. Starting Dose Level and Provisional Dose Levels**

The starting dose is a flat dose of 2.0 mg administered on a 5 continuous days out of 7 days per week intermittent dosing schedule. Provisional dose-escalation levels are listed in [Table 2](#).

### **8.2.4. Definition of Evaluable Subjects**

A subject evaluable for DLT evaluation is defined as one whom, in the DLT evaluation period, either:

- a. Received at least 85% of the planned doses of CC-122 at the cohort-specified dose in Cycle 1 (at least 17 out of 20 doses for the 5 continuous days out of 7 days per week intermittent dosing cohorts), has sufficient data for safety evaluation by the SRC and has not experienced a treatment-related DLT, or
- b. Received at least one dose of CC-122 and experienced a DLT

Non-evaluable subjects will be replaced in the dosing cohort. An additional subject may be enrolled in each dosing cohort to allow for early drop-outs and to avoid study delays after consultation with the sponsor.

Subjects for whom >20% of PK samples were not collected will also be replaced in order to collect sufficient data for PK analysis.

### **8.2.5. Definition of Maximum Tolerated Dose and Non-tolerated Dose**

The non-tolerated dose is defined as the dose level at which 2 or more out of 6 evaluable subjects in any dose cohort experience a DLT.

Once the NTD is identified, dose escalation will be halted.

The MTD is defined as the last dose level below the NTD with zero or one (out of 6) evaluable subject experiencing DLTs during the DLT evaluation period. An intermediate dose (for example, one between the NTD and the last dose level before the NTD) or additional subjects within a dose cohort may be evaluated in order to determine the MTD more precisely.

### **8.2.6. Definition of Dose-limiting Toxicities**

National Cancer Institute Common Terminology Criteria for Adverse Events Version 4.03 will be used to grade adverse events. Events described below will be classified as DLTs.

**Table 8: DLT Criteria**

Toxicity	
Non-hematologic AEs	A clinically relevant non-hematologic AE that is suspected to be related to CC-122 and that commences during the DLT evaluation period and is $\geq$ Grade 3 EXCEPT for: 
 
Grade 3 rash of the acneiform or maculopapular type lasting <math>\leq</math> 4 days (with optimal medical management)
 
Grade 3 diarrhea or vomiting lasting less than 72 hours (with optimal medical management)
 

Laboratory abnormalities	A clinically relevant laboratory abnormality that is suspected to be related to CC-122 and that commences during the DLT evaluation period and is $\geq$ Grade 3
Hematologic	Any febrile neutropenia
	Grade 4 neutropenia lasting $>$ 7 days
	Grade 4 thrombocytopenia lasting $>$ 24 hours or thrombocytopenia of any grade requiring platelet transfusions
	Any Grade 3/4 thrombocytopenia with clinically significant bleeding
Hepatic	Grade 4 liver function tests (LFTs) or Grade 3 ALT with Grade 2 or higher bilirubin will be considered a DLT, irrespective of underlying attribution  However, other Grade 3 LFTs due to disease progression in the liver will not be considered DLTs
Other adverse events	Any adverse event suspected to be related to CC-122 and necessitating a dose reduction during the DLT evaluation period

Toxicities will be considered treatment-related unless clearly attributed to an alternative etiology (for example, tumor progression) by the investigator. Toxicities must be clearly not related to disease progression, medical procedures or intercurrent illnesses in order to be considered dose-limiting.

Isolated laboratory changes without associated clinical signs or symptoms will not be included in this definition. These findings will be discussed and reviewed by the SRC.

### 8.2.7. Criteria for Dose Escalation in the Next Cohort of Subjects

Cohorts will consist of at least 3 or at least 6 evaluable subjects. The decision criteria for dose escalation in any cohort are:

- If no DLT is observed in at least 3 evaluable subjects during the first cycle, the dose will be considered a well-tolerated dose and dose escalation will continue to the next dose level.
- If any DLT is observed in 2 or more of 6 evaluable subjects in the cohort, this dose is considered a non-tolerated dose and dose escalation will discontinue.

- If any DLT is observed in one evaluable subject during the DLT evaluation period, additional subjects will be enrolled to expand the cohort to up to at least 6 evaluable subjects.

The number of cohorts depends on the incidence of DLTs. A subject may experience more than one DLT. Dose-escalation decisions are based on the number of subjects experiencing DLTs.

### **8.2.8. Definition of Stopping Criteria for Dose Escalation**

Dose escalation stops when 2 or more of 6 evaluable subjects at a dose level experience DLTs or the MTD in global CC-122 studies in various indications has been reached.

### **8.2.9. Permitted Dosing Adjustments**

No dose reduction is allowed during the DLT evaluation period, except for subjects who experience DLTs. Subjects who experience DLTs during the DLT evaluation period will be allowed to resume CC-122 at a reduced dose once their toxicity recovers to Grade 1 or baseline, provided recovery occurs within 28 days of interrupting dosing. Dose reductions for non-dose-limiting toxicities are allowed after the DLT evaluation period after consultation with the sponsor.

Those continuing to take CC-122 beyond Cycle 1 may, following approval by the SRC, have their dose level increased, provided that the alternative dose level has been shown to be well-tolerated in at least one cohort of other subjects in this study. In these instances, additional PK evaluations at the higher dose level will be collected.

If a dose reduction is indicated, the next lower dose level will be selected. Two dose reductions are allowed, with the exception of the starting dose for which only one dose reduction is allowed. If any subject continues to experience unacceptable toxicity after 2 dose reductions, CC-122 will be discontinued permanently.

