#### **8.2.9.1. Criteria for Dose Reduction**

Dose reductions are not allowed during the DLT evaluation period, except for subjects who experience DLTs. Subjects who experience toxicities during the DLT evaluation period that do not meet the protocol specified definition for DLTs (Section 8.2.6) may either continue at their assigned dose or withdraw from the study at the discretion of the investigator and/or the subject. If a subject withdraws for any reason other than DLTs prior to the completion of the DLT evaluation period, that subject will be considered non-evaluable and will be replaced.

Once the dosage has been reduced for toxicity for a subject, future escalation will not be permitted.

Any of the AEs listed in [Table 10](#) after the DLT evaluation period will require a dose interruption and/or reduction.

Dose reductions may be considered for AEs occurring after the DLT evaluation period that do not meet the criteria listed in [Table 10](#) after discussion between the investigator and the sponsor.

Guidance for dose reduction is as follows:

- Subjects requiring dose reductions for toxicities occurring on or BEFORE Cycle 1 Day 28 (such as subjects who have experienced DLTs and recovered) should be reduced to the next lowest dose level that has been shown to be tolerated by at least 3/3 or 5/6 subjects.
- Subjects requiring dose reduction for toxicities occurring AFTER Cycle 1 Day 28 may be reduced to the next lowest dose level that has been shown to be tolerated by at least 3/3 or 5/6 subjects.

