Any Grade 4 non-hematologic toxicity, including LFT elevations	
 
• Hold dosing until recovery to Grade <math>\leq 1</math> (or baseline LFT if liver tumors are present)
 
• Reintroduce CC-122 at a lower dose level, if available
 

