Grade 3 or 4 TFR*	
 
Hold CC-122 dosing
 
Initiate therapy with corticosteroids
 
NSAIDs and/or narcotics may also be used as per the investigator's discretion
 
When symptoms resolve to <math><</math> Grade 1, restart CC-122 at the same dose level
 

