**Table 10: Guidelines for Dose Modifications of CC-122 Related Toxicities (Continued)**

Toxicity	Modification
Peripheral neuropathy (neuropathies which begin or worsen while on study) $\geq$ Grade 3	
 
Hold dosing at investigator's discretion
 
When the toxicity resolves to <math>\leq</math> Grade 2 or to baseline, restart CC-122 at the next lower dose level
 

Allergic reaction or hypersensitivity $\geq$ Grade 3	
 
Discontinue CC-122
 

Venous thrombosis/embolism $\geq$ Grade 3	
 
Hold dosing and start anticoagulation therapy; restart CC-122 at the investigator's discretion (maintain dose level)
 

Other $\geq$ Grade 3 non-hematologic toxicity	
 
Hold dosing at the investigator's discretion
 
When the toxicity resolves to <math>\leq</math> Grade 2, restart CC-122 at the same dose level or at the next lower dose level at the investigator's discretion
 

Any non-hematologic toxicity requiring interruption for $> 4$ weeks	
 
Discontinue CC-122
 

Recurrence of Grade 3 non-hematologic toxicity after dose reduction	
 
Reduce dose to the next lower dose level, if available. If a lower dose is not available, discontinue CC-122
 

Recurrence of Grade 4 non-hematologic toxicity after dose reduction	
 
Discontinue CC-122
 

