#### **8.2.9.4.2. Dose Modification and Management of Pneumonitis**

Pneumonitis has been reported with CC-122. The diagnosis should be considered in subjects presenting with nonspecific respiratory signs and symptoms such as hypoxia, pleural effusion, cough, dyspnea, or interstitial pulmonary infiltrates, and in whom infectious, neoplastic and other causes are excluded by appropriate investigations. Subjects should be specifically advised to promptly report any new or worsening respiratory symptoms they experience.

CC-122 dosing for those with radiological features suggestive of noninfectious pneumonitis but with minimal (Grade 1) symptoms may be interrupted per the investigator's discretion. For drug-related Grade 2 pneumonitis, CC-122 treatment should be interrupted and corticosteroids may be indicated. Once symptoms have resolved completely, CC-122 may be reintroduced at the next lower dose level. For drug-related Grade 3 or 4 pneumonitis, CC-122 must be permanently discontinued and corticosteroids used until clinical symptoms have resolved.

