#### **8.2.9.4.3. Dose Modification and Management of Tumor Flare Reaction**

Subjects in this study should be monitored for tumor flare. Tumor flare reaction (TFR) is defined as a sudden and tender increase in the size of the disease bearing sites, including the lymph nodes, spleen and/or the liver often accompanied by low-grade fever, nonpruritic diffuse rash and in some cases increase in the peripheral blood lymphocyte counts. Tumor flare usually occurs within the first cycle of treatment. Tumor flare reaction may mimic progression of disease (PD); however, the TFR will generally subside over time. Therefore, careful monitoring and evaluation is important prior to discontinuing a study subject for PD in the initial cycles of CC-122 therapy.

There are currently no laboratory or radiological tests that distinguish TFR from PD. The distinction should be made on clinical grounds, incorporating observations such as associated physical findings, laboratory findings, and pace of disease before and after institution of treatment. Tumor flare will be recorded as an AE (graded using the NCI CTCAE 3.0 criteria) and not as PD.

Treatment of the TFR is up to the discretion of the investigator, depending on the severity and clinical situation. Recommendations for treatment are outlined in [Table 10](#). Refer to [Table 10](#) for further instructions and dose modifications for Grades 3 and 4 TFR. In mild to moderate cases, it is suggested that CC-122 be continued along with symptomatic treatment as outlined above. In more severe cases, CC-122 should be interrupted, as indicated in [Table 10](#).

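### The permission in Section 8.2.9 to resume CC-122 after a Cycle 1 DLT is not reconciled with the event-specific stopping and restart rules in Section 8.2.9.4 and Table 10

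*Combined protocol and SAP*

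**What the plan says.** **General rule for Cycle 1 DLTs.** Section 8.2.9: "Subjects who experience DLTs during the DLT evaluation period will be allowed to resume CC-122 at a reduced dose once their toxicity recovers". The recovery has to reach Grade 1 or baseline, and do so within 28 days of the interruption. Section 8.2.9.1 adds that subjects who need a reduction for toxicity up to Cycle 1 Day 28 go to the next lowest level already shown to be tolerated.

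**Event-specific rules outside Table 10.** Section 8.2.9.4.2: "For drug-related Grade 3 or 4 pneumonitis, CC-122 must be permanently discontinued". Section 8.2.9.4.1 likewise ends treatment for troponin-T elevation with cardiac symptoms or significant ECG or LVEF change. Neither is limited to a cycle.

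**Table 10.** It calls for discontinuation for Grade 3 or higher pneumonitis, Grade 3 or higher "Allergic reaction or hypersensitivity", desquamating Grade 3 or any Grade 4 rash, and Grade 3 or 4 clinical liver failure. For Grade 3 or higher venous thromboembolism it says "restart CC-122 at the investigator's discretion (maintain dose level"). For Grade 3 or 4 tumor flare it says "restart CC-122 at the same dose level" once symptoms resolve. A separate row, "Any Grade 4 non-hematologic toxicity, including LFT elevations", brings the drug back at a lower level.

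**Scope of Table 10.** Section 8.2.9.1 says that the AEs listed there "after the DLT evaluation period will require a dose interruption and/or reduction". Section 8.2.9.4.3 says "Tumor flare usually occurs within the first cycle of treatment" and refers the reader to Table 10 for its management.

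**Treatment delay.** Section 8.2.9.3, with no cycle limit on restarting, allows the same or a reduced dose at the investigator's discretion or as described in Section 8.2.9.1.

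**The concern.** Table 8 makes nearly every clinically relevant, related non-hematologic AE of Grade 3 or higher that starts in Cycle 1 a DLT. The permission in 8.2.9 therefore reaches events for which other parts of the same section say that treatment ends, and events for which Table 10 keeps the dose unchanged. Two sites could read the protocol differently after the same severe event. One could restart where the other stops, or one could reduce where the other maintains. What is at stake is consistent handling of re-exposure after severe toxicity, and knowing which dose the later safety and response data reflect.

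**Working it through.** No arithmetic applies; the check sets the rules side by side.

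**Step 1: which events are DLTs.** Table 8 excepts only short-lived Grade 3 acneiform or maculopapular rash and short-lived Grade 3 diarrhea or vomiting. When clinically relevant, related and starting in Cycle 1, the events below qualify, with two conditions. The troponin-T rule states no grade, and Table 8 excludes isolated laboratory changes, so that event is a DLT only where it meets Table 8. Tumor flare is graded under CTCAE 3.0 while DLTs are graded under 4.03; I assume a Grade 3 or 4 flare counts.

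**Step 2: the rules compared.** For every event in the table, 8.2.9 permits resumption at a reduced dose.

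| Cycle 1 event meeting Table 8 | Event-specific action | Where stated | Depends on Table 10 applying in Cycle 1? |
|---|---|---|---|
| Pneumonitis, Grade 3 or 4 | Stop permanently | 8.2.9.4.2 and Table 10 | No |
| Troponin-T with cardiac findings, where a DLT | Stop permanently | 8.2.9.4.1 and Table 10 | No |
| Hypersensitivity, Grade 3 or higher | Stop | Table 10 | Yes |
| Desquamating Grade 3 or any Grade 4 rash | Stop | Table 10 | Yes |
| Clinical liver failure, Grade 3 or 4 | Stop | Table 10 | Yes |
| Venous thromboembolism, Grade 3 or higher | Restart, dose maintained | Table 10 | Yes |
| Tumor flare, Grade 3 or 4 | Restart, same dose | Table 10, via 8.2.9.4.3 | Yes, but 8.2.9.4.3 sends flare there |

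**Step 3: does Table 10 apply in Cycle 1?** Section 8.2.9.1 ties its mandatory action to events after the DLT evaluation period, but does not say that the table is inapplicable before then. The table's title and lead-in carry no time limit, and 8.2.9.4.3 uses it for an event expected mainly in Cycle 1. The text supports both readings.

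- *Table 10 applies only after Cycle 1.* The pneumonitis conflict remains, as does the troponin-T conflict where the event is a DLT. Flare is contested. For Cycle 1 hypersensitivity, severe rash and liver failure, no Table 10 stopping rule is left to qualify the permission in 8.2.9.
- *Table 10 applies throughout.* Four event types (pneumonitis, hypersensitivity, severe rash, liver failure), plus troponin-T where it qualifies, meet a stopping rule. Two more (thromboembolism, flare) meet a same-dose rule where 8.2.9 gives a reduced dose and 8.2.9.3 allows either.

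**Step 4: overlap inside Table 10.** At Grade 4 the general non-hematologic row lowers the dose. Six event-specific rows cover the same grade with other actions: flare and thromboembolism keep the dose; rash, pneumonitis, hypersensitivity and liver failure stop treatment. This overlap does not depend on the cycle.

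**Step 5: effect on dose escalation.** Under Section 8.2.4(b), a subject with at least one dose and a DLT is evaluable, whatever happens next. The two-or-more-of-six rule in 8.2.5 and 8.2.7 therefore gives the same answer under every reading.

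**The case against.** The strongest reply is that 8.2.9 is headed as permitted adjustments and only allows resumption, while the pneumonitis and cardiac rules are stricter, more specific and sit in subsections of the same section. Section 8.2.9.4.1 even calls 8.2.9.1 and 8.2.9.3 general guidelines, which suggests that event-specific rules come first. Table 10 also works most naturally that way, since otherwise its Grade 4 row would override the rows beneath it.

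Much of this stands. A reader might infer that the protocol instructs sites to re-expose subjects after Grade 3 pneumonitis, or fixes one outcome for every DLT. The documents do not support that: 8.2.9 is a permission, and a site restarting after such an event would have to disregard 8.2.9.4.2.

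The reply does not settle the matter, however. No passage states the order of precedence. Section 8.2.9 is not among the sections called general, and is itself the specific rule for Cycle 1 DLTs. Putting specific rules first also leaves open whether Table 10 applies in Cycle 1.

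A reader might also infer that these events are likely in this trial. The support is limited. Section 1.1.3 reports interstitial pneumonitis as one of two DLTs among five subjects at 5 mg on the 5/7 schedule, above the highest planned level of 4 mg AIC, and gives no grade. Section 9.1 reports thromboembolic SAEs without grade or cycle. Section 8.2.9.4.3 does not say that Grade 3 or 4 flare in particular occurs in Cycle 1.

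**Conclusion.** The inconsistency is real and should be fixed. It is a fault of wording between sections, not of the design. On any reading, the pneumonitis rule is unreconciled with the permission in 8.2.9, as is the troponin-T rule where that event is a DLT. Three further stopping rules and two same-dose rows join them only if Table 10 applies in Cycle 1, which the protocol leaves unclear. A flat count of five stopping rules and two same-dose rows would be too strong, because it assumes both that Table 10 applies in Cycle 1 and that the troponin-T event always meets Table 8.

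Nor do the documents support any inference that the MTD is at risk: DLT counts and the escalation rule are the same whichever instruction is followed. Scheduled PK sampling ends by Cycle 1 Day 13, apart from sampling delayed by an interruption or repeated after intra-subject escalation, so the primary PK endpoint is barely touched. The consequence is possible inconsistency across the approximately three sites in who is re-exposed after a severe Cycle 1 event and at what dose.

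**What to change.** Reconcile Sections 8.2.9, 8.2.9.1, 8.2.9.3, 8.2.9.4.1 to 8.2.9.4.3 and Table 10 by stating:

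- (a) in 8.2.9, whether the permission to resume after a DLT is subject to the event-specific discontinuation rules;
- (b) in 8.2.9.1 and 8.2.9.4, whether Table 10 applies during the DLT evaluation period;
- (c) whether event-specific rows take precedence over the general rows of Table 10 and over Sections 8.2.9, 8.2.9.1 and 8.2.9.3, covering all six Grade 4 overlaps.

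Which outcome applies to each event is for the sponsor's medical team. The cost is a few sentences in an amendment, with no added subjects, visits or tests.
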